9.4.2 Analysis of the Primary Efficacy Endpoint

The primary efficacy endpoint of time in weeks from baseline to the initial observation closure of a complete wound healing, over 26 weeks, confirmed at two consecutive visits each two weeks apart will be analyzed using the Cox regression analysis (i.e., proportional hazards model) to assess the effect of TTAX01 treatment on time to complete wound healing compared to SC in terms of hazard ratio and difference in the curve of the proportion of subjects reaching the complete wound healing over the 26-week treatment period. For those subjects who discontinue from the treatment period prematurely without wound closure data collected over the confirmation period, those subjects who have missing data of wound closure over the confirmatory period and those subjects whose index ulcers are not deemed to be completely closed at the end of the 26-week treatment period, the time to the closure of a complete wound healing will be considered being censored at the corresponding time point.

The Cox regression model will include the treatment as the main predictor, whereas the subject's baseline index ulcer size and duration will be included in the model as covariates to adjust potential effects on time to wound closure. SAS PROC PHREG will be used to conduct the Cox regression analysis. The estimated hazard ratio of SC plus TTAX01 arm vs, SC alone arm and its 95% confidence intervals (CI) for wound healing will be reported.

For summary statistics and graphic illustrations of the primary efficacy endpoint, the obtained proportion of subjects with complete wound healing, the estimated median of time in weeks to the complete wound healing and the 95% CI as well as the estimated probabilities at each of

the 26 weeks of index ulcer non-closure will be analyzed and reported for each of the two treatment arms, using the method of Kaplan-Meier survival analysis with SAS PROC LIFETEST.

The analysis of the primary efficacy endpoint will be performed for the ITT population and PP population.

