3 OBJECTIVES AND ENDPOINTS

OBJECTIVES	ENDPOINTS	JUSTIFICATION FOR ENDPOINTS			
Primary					
To determine whether treatment of high grade DFU with standard care plus TTAX01 results in a higher probability of achieving complete wound closure over 26 weeks, compared with standard care alone.	Time from baseline to initial observation of healing, over 26 weeks, where healing has been confirmed at two consecutive visits each two weeks apart.	The endpoint complies with FDA guidance. Dropouts should be minimal during the first 26 weeks, but may increase thereafter. Analysis will use a Cox proportional hazard model			
Secondary					
To compare differences between treatment groups in proportions of wounds healed through 50 weeks	Proportions of wounds healed by Week 50	This endpoint provides insight into longer term benefits of the intervention			
To compare long term durability of closure between treatment groups	Proportions of wounds that re-ulcerate by Week 50	May provide insight into the quality of healing			
To compare limb preservation between treatment groups	Proportions of minor (portions of the foot) and major (ankle, above or below the knee) amputations following the initial procedure by Week 50	Each amputation risks loss of mobility, with consequent increased mortality			
To compare patient reported mobility (lower extremity function) between groups.	Total score on PROMIS Health Organization Neuro- QoL "Lower Extremity Function" at Study End.	The tool is an NIH validated measure of patient reported outcomes			
Safety					
To examine Quality of Life endpoints related to therapeutic intervention	Total score of quality of life assessment determined by Cardiff Wound Impact Schedule (CWIS) at Study End				
Proportion of subjects experiencing adverse events, by group	Spontaneously reported and elicited adverse events, coded in MedDRA				

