Subjects whose wounds close at any time during the trial will move to a series of two consecutive confirmation of closure visits, two weeks apart, then continuing with monthly observational visits until the end of the study, unless the first observation of closure is at the final visit, in which case their participation in the study will extend out to 54 weeks, moving to a series of two consecutive confirmation of closure visits, two weeks apart.

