6.5 Concomitant Therapy

In this study, the term Concomitant Medication is inclusive of all medications and therapies.

The following is excluded throughout the entire study:

• Canagliflozin, a type 2 diabetic medication, also referred to as Invokana, Invokamet, and Invokamet XR

The following are excluded through W26 (Visit 23):

- Topical antibiotics and antiseptic agents including hydrogen peroxide, acetic acid, chlorhexidine, povidone/iodine, and cetrimide
- Enzymes, negative pressure wound therapy, hyperbaric oxygen, growth factors and tissue products containing growth factors (e.g., Oasis[™]), living skin, cellular products (e.g., Apligraf[™], Dermagraft[™]), amniotic membrane and umbilical cord products
- Powdered collagen dressings (e.g., Cellerate[™]), formulated collagen dressings (e.g., Excellagen[™])
- Hyaluronic acid products (e.g., Hyalomatrix[™])
- Revascularization procedures (e.g., endoscopic perforator surgery, superficial venous ablation, endovenous laser ablation, valvuloplasty, free flap transfer with microvascular anastomoses)
- Achilles tendon lengthening

The following therapies are excluded before Visit 9 (Day 57), but allowed thereafter if the wound area is \leq 50% closed relative to the post debridement wound measurement obtained prior to randomization:

- Silver-containing products (e.g., Aquacel Ag[™], Mepilex Ag[™], Acticoat[™])
- Collagen dressings (e.g., Integra Omnigraft™, Promogran Prisma™, Puracol™, Fibracol™)

Systemic anti-microbials may be used as prescribed. Wound cleansing with a neutral, non-irritating and non-toxic solution is recommended at the discretion of the Investigator. Sterile saline, non-ionic cleanser, or hypochlorous acid are recommended.

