8.1.7 Long Term Observation Period (Visits 24 – 28; 28 ± 4 days)

[Purpose] To evaluate safety and observe wound status

No further applications of TTAX01 are permitted beyond Visit 16. Subjects enter this Long Term Observation Period whether they have not completely healed their wound, or, they have achieved complete closure. If they have achieved complete wound closure, where healing has been confirmed at two consecutive visits each two weeks apart, but their wound re-opens during this period, it will be regarded as a failure of durable healing.

If at any Long Term Observation Visit a previously unhealed index ulcer is observed to be closed, perform the following procedures:

- Assess adverse events
- Review concomitant medications
- Assess subject compliance regarding off-loading since the last visit
- Obtain photographs of the closed ulcer using the electronic wound imaging and measuring device
- Observe the wound if it is fully epithelialized with no drainage or need for a dressing, record it as closed.

The next visit scheduled will serve as the first consecutive confirmation visit in 14 ± 2 days and will begin the confirmation of closure procedures (refer to Section 8.1.9).

Otherwise,

- Assess adverse events
- Review concomitant medications. These will be recorded in the subject's source document, but should only be recorded in the eCRF for the following:
 - All current and past treatments for the index ulcer only
 - Concomitant medications used to treat the index ulcer (e.g., systemic antibiotics for an index ulcer infection) and the peri-ulcer area (such as treatment for erythema, irritation, itching), together with the indication for the medication

- Concomitant medications used to treat all SAE, and all AE considered "RELATED" to the product will be recorded in the appropriate eCRF.
- Assess the foot and lower extremity, then assess the index ulcer after removal of the dressing.
 - Determine whether skin and soft tissue infection (SSTI) is present. If SSTI is present, without evidence of osteomyelitis, obtain a deep tissue biopsy for histopathology, culture and sensitivity, and adjust the antibiotic regimen (start a 2 week course of antibiotics if none are being taken, or revise antibiotics if still being taken for a previous infection)

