8.1.9 Confirmation of Closure ("C" Visits)

[Purpose:] These visits serve to confirm that a wound has achieved complete closure

Confirmation of Closure visits are used to record the initial observation of closure, and persistent closure. Ideally, a wound that shows initial closure will still be closed at a confirmation visit two weeks later, and at a second confirmation visit four weeks later. At each of the confirmatory visits, use the Confirmation of Closure visit form(s) to record observations. Continue with the off-loading device appropriate to the location of the ulcer during the period of confirmatory visits.

Perform the following procedures:

- Assess adverse events
- Review concomitant medications
- Assess subject compliance regarding off-loading since the last visit

- Obtain photographs of the ulcer using the electronic wound imaging and measuring device
- Observe the wound if it is fully epithelialized with no drainage or need for a dressing, record it as closed.

If the wound is found to be open at either confirmation visit or if the subject misses a scheduled confirmation visit, record it as such and then move directly to the original schedule of visits. This may become a treatment visit for example if the subject has not passed Visit 16, or an observation visit if the subject has passed Visit 16.

If the index ulcer is closed at the first confirmation visit, schedule the subject to return for a second consecutive confirmation visit in 14 ± 2 days. If the index ulcer remains closed at the second confirmation visit, schedule the subject to begin the Long Term Observation Period at the next study day that will put the subject onto the planned 28 day schedule of visits. For example, if a subject completes the second confirmation visit on Day 50, they should return on Day 64 and continue thereafter with visits every 28 ± 3 days. Days 92, 120, 148, 176, 204, or 232 are the other days on which these subjects can enter into Long Term Observation. Note that Day 176 has a unique window of plus or minus 2 days, otherwise these visits have windows of plus or minus 3 days.

If the initial closure is observed at Visit 28 or 29, the subject should move immediately to the End of Study procedures once both confirmation visits are completed, or if the wound is found to be open at either of the two confirmatory visits.

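### The third censoring clause in Section 9.4.2 goes by ulcer status at the end of Week 26: taken literally it censors confirmed closures that re-opened, and it leaves first closures at Visits 22 and 23 unsettled

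*Protocol*

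**What the plan says.** **Event.** Protocol Section 3 defines the primary endpoint as "Time from baseline to initial observation of healing, over 26 weeks, where healing has been confirmed at two consecutive visits each two weeks apart". Sections 1.1 and 9.1 and the opening sentence of 9.4.2 agree: the event is dated at the first observed closure, on condition that two later visits confirm it.

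**Censoring.** Section 9.4.2 then lists three censored groups: early discontinuations without confirmation data, subjects with missing confirmation data, and "those subjects whose index ulcers are not deemed to be completely closed at the end of the 26-week treatment period". For all three, the time to closure "will be considered being censored at the corresponding time point".

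**Confirmation.** The stated purpose of the C visits in 8.1.9 is: "These visits serve to confirm that a wound has achieved complete closure". The first is two weeks after the initial closure, and the wound should still be closed "at a second confirmation visit four weeks later". Section 4.1 sets no calendar limit: "Subjects whose wounds close at any time during the trial will move to a series of two consecutive confirmation of closure visits, two weeks apart".

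**Re-opening.** Section 8.1.7 covers subjects in long-term observation: "If they have achieved complete wound closure, where healing has been confirmed at two consecutive visits each two weeks apart, but their wound re-opens" in that period, this is a failure of durability. Section 9.1 makes re-ulceration a secondary endpoint among subjects already healed.

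**The concern.** The endpoint asks whether a confirmed first closure occurred at any time in the window. The third censoring clause asks what state the ulcer is in when the window ends. The answers can differ for two groups.

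- **Confirmed closures that re-open before Week 26.** The endpoint counts them as events at first closure. The clause, as written, censors them.
- **First closures at Visit 22 or 23.** They cannot be fully confirmed by Week 26. Whether they count depends on what being deemed completely closed means at that date.

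At stake are the event count, the reported healed proportions and some power in the primary analysis of a trial whose site staff are not blinded. If re-opened wounds are censored, the durability outcome also leaks into the primary endpoint.

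**Working it through.** **1. Visit calendar.** Weekly visits from Day 1 put Visit 20 on Day 1 + 7 × 19 = 134. Two-week steps give Visits 21, 22 and 23 on Days 148, 162 and 176. Section 6.5 equates Visit 23 with Week 26. The C visits come 14 and 28 days after first closure:

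| First closure | First C visit | Second C visit | Confirmed by Visit 23? |
|---|---|---|---|
| Visit 21, Day 148 | Day 162 | Day 176 | yes |
| Visit 22, Day 162 | Day 176 | Day 190 | no |
| Visit 23, Day 176 | Day 190 | Day 204 | no |

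**2. Re-opened wounds, text against text.** Take a wound first closed at Week 12, confirmed by Week 16 and open again at Visit 23. By Section 3 it is an event at Week 12. By the third clause of 9.4.2 it is not closed at the end of the period and is censored. Section 8.1.9 lets confirmed subjects enter long-term observation as early as Day 64, so the durability rule in 8.1.7 already covers re-openings before Week 26. That rule, 8.2 and 9.1 all treat re-opening as a later, separate outcome, which implies that the healing event stands.

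**3. The plan's sample size, reproduced.** Inputs from Section 9.2: 40% and 65% healed, 90% power, 10% dropout, 1:1 allocation.
- HR = ln(0.35)/ln(0.60) = 2.055.
- Freedman events = (1.960 + 1.282)² × (3.055/1.055)² = 88.1.
- Per arm: 88.1/(0.40 + 0.65) = 83.9, and 83.9/0.9 = 93.2, so 94 as stated. This uses two-sided 0.05, as in 9.4.1; it is the level at which the stated 94 reproduces.
- At 110 per arm: 110 × 0.9 × 1.05 = 104.0 events, power 94.1% (plan: 94%).
- At 125 per arm: 118.1 events, power 96.4% (plan: 97%).

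**4. Excluding late first closures.** Assumption: exponential healing that reaches 40% and 65% at Week 26. Confirmation takes four weeks, so the last qualifying first closure is at Week 22.
- Control: 1 − 0.60^(22/26) = 35.1%, a loss of 4.9 points (12.3% of events; about 6 of 125 subjects).
- TTAX01: 1 − 0.35^(22/26) = 58.9%, a loss of 6.1 points (9.4% of events; about 8 of 125 subjects).
- Treatment difference: 25.0 points becomes 58.9 − 35.1 = 23.8.
- Events at 110 per arm: 93.0, power 91.5%. At 125 per arm: 105.7, power 94.4%.

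If the cut-off is instead Visit 21 (Day 148) against a full 26 weeks, the losses are 6.2 and 7.8 points and power is 90.6% and 93.7%. Under this model the hazard ratio stays at 2.055 throughout.

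**5. Censoring re-opened wounds.** The protocol gives no re-opening rate, so 10%, 20% and 30% of confirmed closures per 26 weeks are assumed. A log-rank simulation on the visit grid (110 per arm, 10% dropout) gave power of about 95%, 91% and 89%, against about 96% with no re-opening. At 20%, about 3 control and 6 TTAX01 events were censored. With late closures also excluded, power at 20% was about 90%.

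The simulated baseline exceeds the 94.1% in step 3 because Freedman's formula is the more conservative: Schoenfeld's formula on the same 104.0 events gives √104.0 × ln(2.055)/2 − 1.96 = 1.71, or 95.7%.

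**The case against.** The best defence reads the clause in context. The sentence just before it restates the endpoint as a confirmed first closure, and censoring ordinarily applies to subjects without the event. The third group can then be taken as ulcers that never reached closure by Week 26. Re-ulceration has its own endpoint. Where the protocol wants a sustained state it says so, as in 9.4.3, which asks that ulcers achieve and remain healed at Week 50. This reading is sensible and is probably what was meant, but it is not what the clause says. Section 9.4.3 also shows Section 9.4 moving from an event (healed by Week 50, in Section 3) to a status, so a status reading is not far-fetched.

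A reader might go further and infer that both groups are definitely events under one rule and censored under the other, with Visit 21 the last first closure that can count. The documents do not support that. If the clause goes by wound state, an ulcer first closed at Visit 22 or 23 and still closed is closed at Week 26 and is not censored. It is censored only if completely closed means confirmed by then. Sections 8.1.7 and 8.1.9 allow that meaning; 4.1 and 8.1.9 point against it by running C visits at any time, even beyond the final visit. The Phase 2 design does not settle the matter, since Section 2.1 names the primary endpoint's length and analysis as what changed.

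It is also fair that 9.4.1 leaves data conventions to the SAP, which was not available here and may resolve this. The censoring rule is nonetheless already written in the protocol.

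**Conclusion.** The point holds in two parts of different strength. Taken literally, the clause contradicts the endpoint for wounds with a confirmed closure that re-open before Week 26. For first closures at Visits 22 and 23 it is ambiguous only.

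The effect is modest. The late-closure reading costs about 2 to 3.5 power points and moves both arms' healed proportions down together by 5 to 8 points, given exponential healing at the planned rates. It does not change the hazard ratio under that model, so a claim that this reading shifts the estimated effect is not shown. The cost of censoring re-opened wounds rests wholly on assumed rates. It removes more TTAX01 than control events in number, which works against the product. The main reason to act is that the primary event should not depend on how one clause is read.

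**What to change.** Replace the third censoring clause of 9.4.2 with:

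> Subjects with no closure first observed on or before Visit 23 and confirmed at both C visits (including C visits after Visit 23) are censored at their last wound assessment on or before Visit 23. Re-opening after a confirmed closure does not revoke the event and is analysed as re-ulceration.

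Use the same rule for the Kaplan-Meier estimates and carry it into the SAP. Under this rule the sample size in 9.2 stands. No new visits or data are needed: C visits after Visit 23 are already provided for, and follow-up runs to Week 50. The one cost is that the last primary events become final about four weeks after Visit 23.

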9.4.3 Analysis of the Secondary Endpoints

Secondary efficacy endpoints in this study include proportions of index ulcer healed by Week 50, proportions of wound re-ulcerations by Week 50, proportions of minor and major amputations by Week 50, and total score of PROMIS Lower Extremity Function Questionnaire at end of study.

The non-parametric Cochran-Mantel-Haenszel (CMH) test with adjustment for baseline wound size cohort will be used to examine treatment effects for the SC plus TTAX01 arm vs. SC alone arm on proportion of subjects with index ulcer achieving and remaining healed at Week 50, proportion of subjects (among those with complete wound healing before Week 50) with wound re-ulceration at Week 50, and proportion of subjects with minor and/or major amputations by Week 50. Subjects' missing values at Week 50 in these endpoints, due to either no assessment or early termination from the study, will be imputed using the last-observation carry forward (LOCF).

An analysis of covariance model (ANCOVA) with treatment and baseline wound size as effect will be used to analyze total score of PROMIS Lower Extremity Function Questionnaire at end of study. Subjects' missing values in this endpoint, due to either no assessment or early termination from the study, will utilize the assessment collected at the early termination visit.

The analyses of the secondary efficacy endpoints will be performed for the ITT population and PP population as well as the LO population.

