9 STATISTICAL CONSIDERATIONS

9.1 Statistical Hypotheses

• Primary Efficacy Endpoint(s):

The primary efficacy endpoint is time in weeks from baseline to the initial observation closure of a complete wound healing, over 26 weeks, that is confirmed at two consecutive visits each two weeks apart. The primary efficacy endpoint will be analyzed using the Cox regression analysis (i.e., proportional hazards model) to assess the effect of TTAX01 treatment on time to complete wound healing compared to SC in terms of hazard ratio and difference in the curve of the proportion of subjects reaching the complete wound healing over the 26-week treatment period.

The null hypothesis is that the hazard ratio of TTAX01 arm vs, SC arm is not statistically different from 1.0. The alternative hypothesis is that the hazard ratio is lower than 1.0 at the significance level of <0.05.

• Secondary Efficacy Endpoint(s):

Secondary efficacy endpoints in this study include proportions of index ulcers healed by Week 50, proportions of wound re-ulcerations by Week 50, proportions of minor and major amputations by Week 50, and total score of PROMIS Lower Extremity Function Questionnaire at end of study.

For index ulcer healing by Week 50, the null hypothesis is that the proportion of subjects with wound healing will not be statistically different between the two treatment arms of this study at Week 50. The alternative hypothesis is that a greater proportion of subjects in the SC plus TTAX01 arm will have index ulcers healed at Week 50, compared to the SC alone arm.

For index ulcer re-ulceration by Week 50, the null hypothesis is that, among those subjects who have had the index ulcer healed before Week 50, the proportion of subjects with wound re-ulcerated will not be statistically different between the two treatment arms of this study at

Week 50. The alternative hypothesis is that a smaller proportion of subjects in the SC plus TTAX01 arm will have index ulcers re-ulcerated at Week 50, compared to the SC alone arm.

For minor and major amputations by Week 50 following initial procedure, the null hypothesis is that the proportion of subjects receiving minor and/or major amputations will not be statistically different between the two treatment arms of this study by Week 50. The alternative hypothesis is that a smaller proportion of subjects in the SC plus TTAX01 arm will have minor and/or major amputations by Week 50, compared to the SC alone arm.

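### The Week 50 healing endpoint is defined as healed by Week 50 but tested as healed and still healed at Week 50

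*Protocol*

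**What the plan says.** **Healing.** The objectives table in Section 3 gives the endpoint as "Proportions of wounds healed by Week 50"; the synopsis (Section 1.1) uses the same cumulative form. Section 9.4.3 opens by listing "proportions of index ulcer healed by Week 50". Its next paragraph applies the CMH test to the "proportion of subjects with index ulcer achieving and remaining healed at Week 50". Section 9.1 introduces the hypothesis as concerning healing by Week 50, then states the alternative as "a greater proportion of subjects in the SC plus TTAX01 arm will have index ulcers healed at Week 50".

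**Re-ulceration.** Section 3 lists "Proportions of wounds that re-ulcerate by Week 50" under a separate objective, long-term durability of closure. Section 9.4.3 tests the proportion of healers "with wound re-ulceration at Week 50". Amputation, in that same sentence of Section 9.4.3, stays cumulative.

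**Re-opening.** Section 8.1.7 says of subjects whose closure was confirmed: "but their wound re-opens during this period, it will be regarded as a failure of durable healing". Section 8.2 says that re-opening after confirmed closure is assessed by single observations.

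**The concern.** By Week 50 asks whether an event ever happened. Achieved and remaining at Week 50 asks about state on one date and adds a condition that Sections 1.1 and 3 do not contain. The two rules disagree on one identifiable group: subjects with confirmed closure whose wound is open at Week 50. The protocol expects such subjects, because it makes re-ulceration an endpoint.

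Two things are at stake. First, one re-opening can count against a subject twice, as not healed in one secondary endpoint and as re-ulcerated in the next, although Section 3 separates healing from durability. Second, the estimate and p-value for the first secondary endpoint can depend on which rule is applied. The trial is open label (Section 6.3), so the rule should be fixed before outcomes are known.

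**Working it through.** **Step 1: the same wound under each rule.**

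| Course of the index ulcer | Sections 1.1 and 3 (by) | Section 9.4.3 test (remaining, at) |
|---|---|---|
| Confirmed closure, still closed at Week 50 | healed | healed |
| Never confirmed closed | not healed | not healed |
| Confirmed closure, later re-opened, open at Week 50 | healed | not healed |

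Only the third row differs. A subject in that row may already have counted as an event in the primary 26-week analysis.

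**Step 2: the arithmetic link.** Let *p* be the proportion ever healed in an arm and *r* the share of those healers open at Week 50. Then

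- by: difference = p_T − p_C
- remaining at: difference = p_T(1 − r_T) − p_C(1 − r_C)

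If r = 0 in both arms, the two coincide. If r is equal and above 0, the difference shrinks by the factor (1 − r). If p_C·r_C exceeds p_T·r_T, the difference grows.

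**Step 3: illustration.** The protocol gives no figure for this contrast, so there is none to reproduce. Inputs:

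- 125 per arm: 250 in total (Section 1.1), randomised 1:1 (Section 9.2).
- Two-sided 5% level (Section 9.4.1).
- TTAX01 ever healed 65%: the Section 9.2 planning value, set for the primary endpoint and borrowed here. 0.65 × 125 = 81.
- Control ever healed: 50% (an assumption; 62.5, taken as 62), or 42.5%, the one-year closure figure from the real-world database in Section 2.2 (53).
- Share of healers open at Week 50: not in the protocol; assumed 0 to 30%.

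Test: pooled two-proportion z, an unstratified stand-in for the CMH test, with z = (x_T − x_C)/n ÷ √[p̄(1 − p̄)·2/n].

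By, 81 versus 62: p̄ = 143/250 = 0.572; SE = √(0.572 × 0.428 × 2/125) = 0.0626; z = 0.152/0.0626 = 2.43; p = 0.015.

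Remaining at, 20% of healers open in each arm: 81 − 16 = 65 and 62 − 12 = 50; p̄ = 115/250 = 0.460; SE = 0.0630; z = 0.120/0.0630 = 1.90; p = 0.057.

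| Ever healed (TTAX01 vs control) | Healers open at Week 50 (TTAX01 / control) | Healed under the test | Difference (points) | p |
|---|---|---|---|---|
| 81 vs 62 | 0% / 0% (same as by) | 81 vs 62 | 15.2 | 0.015 |
| 81 vs 62 | 10% / 10% | 73 vs 56 | 13.6 | 0.031 |
| 81 vs 62 | 20% / 20% | 65 vs 50 | 12.0 | 0.057 |
| 81 vs 62 | 30% / 30% | 57 vs 43 | 11.2 | 0.071 |
| 81 vs 53 | 0% / 0% (same as by) | 81 vs 53 | 22.4 | 0.0004 |
| 81 vs 53 | 20% / 20% | 65 vs 42 | 18.4 | 0.0033 |
| 81 vs 53 | 30% / 10% | 57 vs 48 | 7.2 | 0.25 |
| 81 vs 53 | 10% / 30% | 73 vs 37 | 28.8 | <0.0001 |

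**Step 4: re-ulceration.** By and at differ here only for a wound that re-opened after confirmed closure and has closed again by Week 50. If 30% of healers re-ulcerate and half of those wounds have re-closed (both assumed), by gives 30% and a literal at gives 15%. Whether the protocol means the literal at is taken up below.

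**The case against.** **Section 9.4.3 may simply be the more specific rule.** Section 3 does not say that healing counts regardless of later re-opening, and durable healing is a legitimate endpoint. It is true that either rule could be chosen. But Section 9.4.3 uses both within two paragraphs, and the rest of the protocol leans cumulative: durability is a separate objective, Section 8.1.7 calls a re-opening a failure of durable healing rather than of healing, and the re-ulceration test takes as its denominator everyone who healed before Week 50.

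**The statistical analysis plan will settle it.** Section 9.4.1 leaves methods and data conventions to that plan. Either choice there would still contradict part of the protocol, so the protocol itself needs correcting.

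**A reader might infer that the re-ulceration endpoint is contradicted just as badly.** The text does not support that. The conflict is one preposition. Section 8.1.7 makes no exception for a wound that closes again, and Section 8.2 makes one observation of re-opening sufficient. Sections 8.1.7 and 8.1.8 also begin confirmation visits only for a previously unhealed ulcer, so they give no explicit route from re-opening back to confirmed closure.

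**A reader might take last-observation-carried-forward imputation as proof of a status endpoint.** It is not: the same clause covers amputation, which is tested cumulatively.

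**A reader might conclude that the switch always costs power, or will be exploited.** Neither follows. With less re-ulceration on TTAX01, which is the protocol's own alternative hypothesis, the tested difference can be the larger one. Nothing in the document suggests intent.

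**Conclusion.** For healing, the stated endpoint and the stated test contradict each other in the current text. The two rules can give different results; they do so only if some wounds with confirmed closure are open at Week 50. The effect has no fixed direction: from 22.4 points under by, the illustrations give 7.2 to 28.8 points. From 81 versus 62 ever healed, equal 20% re-ulceration moves p from 0.015 to 0.057. These sizes rest on assumed healing and re-ulceration rates and an unstratified test; the contradiction itself rests on the wording alone.

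For re-ulceration there is a lesser wording conflict, and Sections 8.1.7 and 8.2 favour the any-time reading. The primary endpoint and its Cox analysis are not touched. The correction should be made because it is cheap and concerns the first secondary endpoint listed, but it does not threaten the trial's main conclusion.

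**What to change.** In Sections 9.1 and 9.4.3, test the endpoints as Sections 1.1 and 3 define them:

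- **Healed by Week 50:** confirmed closure first observed on or before Visit 29, regardless of later re-opening. Section 4.1 already provides confirmation visits to Week 54 for closures first seen at the final visit.
- **Re-ulcerated by Week 50:** any re-opening after confirmed closure up to Visit 29, even if the wound closes again.
- **Supportive endpoint, separately named:** confirmed closed and still closed at Visit 29.

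Sections 1.1 and 3 already use the cumulative wording and need at most the explicit definitions. Cost: a wording amendment to Sections 9.1 and 9.4.3. Wound status is already assessed at every scheduled visit, so no new data, visits or subjects are needed.
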